To compare rates of mechanical ventilation between Plasma Exchange (PEX) and control groups in patients with severe COVID requiring CPAP/ NIV at treatment onset

To compare rates of clinical thrombotic events either venous (deep vein thrombosis DVT or pulmonary embolism PE) or arterial thrombus (cardiac, neurological and peripheral vascular) between Plasma Exchange (PEX) and control groups in patients with severe COVID

To compare reduction in the inflammatory-thrombotic response by monitoring von Willebrand factor VWF antigen/ADAMTS 13 activity ratio between Plasma Exchange (PEX) and control groups in patients with severe COVID

To compare the stability of cardiac function based on echocardiogram/troponin/BNP measurements between Plasma Exchange (PEX) and control groups in patients with severe COVID

To compare incidence of acute kidney injury as defined by KDIGO criteria between Plasma Exchange (PEX) and control groups in patients with severe COVID

To compare mortality at day 28 between the PEX and control groups

6 Trial design

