9.1 Pre-treatment Assessments

All cases screened for the study will be captured and reason for not being recruited documented.

The following trial specific procedures will be carried out after consent:

1. Demographics recorded including gender, age, height, weight, race
2. Medical History recorded to exclude underlying pre morbid conditions, VTE history, Smoking history
3. General physical examination
4. Concomitant Medication recorded: Primarily antibiotics, noradrenaline use
5. Blood tests
 - Serum pregnancy test (for women of child bearing potential) in last 7 days
 - Baseline inflammatory parameters and routine bloods (FBC, renal, liver function and coagulation screen with fibrinogen, LDH, CRP, D dimer, ferritin)
 - Hepatitis A, B, C and HIV pre PEX (result does not need to be available before PEX)
 - Troponin T/BNP (result does not need to be available before PEX)
 - C3/4 (result does not need to be available before PEX)
 - Autoimmune screen (ANA, ENA) (result does not need to be available before PEX)
 - Factor VIII, VWF, ADAMTS-13 activity (result does not need to be available pre PEX)
 - IgG and IgM to COVID-19 (result does not need to be available before PEX)
 - PCR result for COVID-19 (result does not need to be available before PEX, see inclusion criteria for definition of probable COVID))
6. Respiratory parameters: SaO₂, RR
 - PaO₂, FiO₂
 - Method of assisted ventilation eg HDNOHFNO, CPAP
 - P:F ratio
 - CXR/ CT/HRCT : if undertaken as part of routine clinical care
7. Cardiac investigations
 - ECG (result does not need to be available before PEX)

- Echocardiography (if available within 48 hours of enrolment to study)

The results from the following routine procedures may be used:

Blood test results within 48 hours of enrolment

PCR result for COVID-19 within past 14 days (result does not need to be available before PEX, see inclusion criteria for definition of probable COVID)

Pregnancy test within 7 days

Where routine results are not available, the procedure(s) will be carried out at screening after consent.

All pre-treatment procedures will be carried out as specified in the schedule of assessments (**appendix 2**).

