9.4 Subsequent assessments and procedures

9.4.1 Visit schedule and assessments

A schedule of all trial assessments and procedures is set-out in **Appendix 3**.

Day 1- 5

- eligibility check pre PEX if randomised to PEX
- Vitals pre and post PEX (temperature, blood pressure, pulse, respiratory rate and oxygen saturation level) or once daily
- Plasma exchange if randomised to PEX
- assessment of compliance with PEX
- general physical examination
- recording of relevant concomitant medications eg start stop dates of antibiotics, noradrenaline
- Daily routine bloods (FBC, renal, liver function and coagulation screen with fibrinogen)
- Inflammatory markers on D1,D3 &D5 (LDH, CRP, D dimer, ferritin)
- Citrated plasma and serum samples pre and post PEX, or daily for those randomised to SOC to save for VWD screen, ADAMTS13 activity, COVID-19 serology, and multiplex inflammatory markers related to ILs cytokines, interferons, and vascular markers of endothelial injury. Spare samples can be used for COVID-19 related research as authorised by the trial team
- Respiratory parameters: Oxygen requirement, respiratory rate, type of ventilator support-as part of standard of care assessment
- Echocardiogram on D1
- Troponin and BNP on D1
- adverse event collection
- Reactions to Plasma exchange: graded 1-4
- Complications related to central vascath
- Need for antibiotics
- Deterioration requiring ventilation
- Arterial or venous thrombotic event

Reassessment (Day 5-7)

Review of clinical and laboratory parameters by trial team. Consideration of further 5 day block of PEX if clinical and biochemical improvement following initial 5-day block but persistent pro-thrombotic phenotype

*If a patient has a second 5 days of PEX started-follow instructions for day 1-5 above

Follow up Day 6 - 28*

- Vitals (temperature, blood pressure, pulse, respiratory rate)
- general physical examination-weekly
- recording of concomitant medications-related to antibiotics, new cardiac medication, but not all the routine medicines re SOC and not including PRN medications.
- Daily routine bloods (FBC, renal, liver function and coagulation screen with fibrinogen)
- Inflammatory markers, at least 3 x/week (LDH, CRP, D dimer, ferritin)

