- Citrated plasma and serum samples taken at least weekly to 28 days to save for VWD screen, ADAMTS 13 activity, COVID-19 serology, and multiplex inflammatory markers related to ILs cytokines, interferons, and vascular markers of endothelial injury. Spare samples can be used for COVID-19 related research as authorised by the trial team
- Respiratory parameters
- Echocardiography D7
- Troponin/BNP weekly D7, D14, D21, D28
- Adverse event collection
- Need for antibiotics
- Deterioration requiring ventilation
- Arterial or venous thrombotic event

End of study Day 28

- 28 day mortality and outcomes
- Echocardiogram, if available, D28

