12.1.2 Secondary outcomes

1. Number of patients requiring mechanical ventilation who required only supplemental O₂/CPAP at study entry. This will be captured throughout the period of the study, by review of the oxygen requirements and ventilatory support required throughout the study (O₂ requirement or PaO₂:FiO₂ (P:F ratio) sequentially)
2. 50% decrease in VWFAg/ADAMTS 13 activity ratio from baseline to end of PEX.
3. Prevent deterioration in myocardial function on ECHO/ cardiac parameters -monitoring of cardiac function through echocardiogram and/ or BNP and Troponin levels throughout study period
4. Clinical thrombotic events documented by imaging either venous DVT/PE, or arterial thrombus (cardiac, neurological and peripheral vascular) throughout the study period
5. Incidence of acute kidney injury as defined by KDIGO criteria throughout study period
6. Mortality at 28 days

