12.4.3 Secondary outcome analysis

Secondary outcomes will be summarised and compared using suitable statistical methods. For example, binary outcomes may be compared using chi-squared tests and numerical outcomes may be compared using t-tests. P-values from tests of secondary outcomes may be adjusted to account for multiple testing. Appropriate regression methods will be used to perform adjusted analyses or to account for repeated measures.

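### Secondary outcome 3 (cardiac function) names no common measure, time point or combining rule, so patients can be scored on different tests; report each component separately, with troponin and BNP adjusted for baseline

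*Combined protocol and SAP*

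**What the plan says.** Section 12.1.2, item 3, sets the aim of preventing a decline in heart function, assessed by "monitoring of cardiac function through echocardiogram and/ or BNP and Troponin levels throughout study period". The matching objective in Section 5 is "To compare the stability of cardiac function based on echocardiogram/troponin/BNP measurements between Plasma Exchange (PEX) and control groups in patients with severe COVID". Neither deterioration nor stability is defined anywhere.

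The schedule for the three components is uneven:

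- **Echo before treatment (Section 9.1):** "Echocardiography (if available within 48 hours of enrolment to study", so conditional.
- **Echo on Day 1 and Day 7 (Section 9.4.1):** "Echocardiogram on D1" and "Echocardiography D7", both without condition.
- **Echo on Day 28 (Section 9.4.1):** "Echocardiogram, if available, D28", so conditional. Appendix 3 marks a combined ECG/echo row on Days 1, 7 and 28 with no condition.
- **Troponin and BNP (Section 9.4.1):** Days 1, 7, 14, 21 and 28, without condition and in both arms. Appendix 3 also marks Day 5.

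Section 12.4.3 assigns no analysis to this outcome. It offers examples, among them that "numerical outcomes may be compared using t-tests", and adds that regression will be used for adjusted or repeated-measures analyses. Section 6.1 says the trial is unblinded to investigators and patients.

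**The concern.** An outcome that can be met on echo, on BNP and troponin, or on both is not one outcome. A patient with no usable echo is judged on blood markers alone, and a patient with all three tests can deteriorate in more ways. If the number of tests differs between arms, the apparent event rates differ even when the hearts do not. Investigators know the allocation, so who is scanned, and which measure is put forward, can both follow from that knowledge. Nothing suggests this is intended, but the text does not prevent it.

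The outcome also carries more weight than its place in the list suggests. Section 10.5 treats cardiac disease such as arrhythmia and right heart failure as anticipated events that need not be captured as adverse events, unless a relation to the product cannot be ruled out. Item 3 is then the main structured comparison of cardiac function between the arms.

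A second, smaller matter is the analysis. The only method named for a numerical outcome is a t-test. If that were applied to raw follow-up values of a right-skewed marker, it would ignore both the skew and the baseline value already being collected.

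**Working it through.** **1. The plan's own power figures.** Section 12.2.1 gives power for the primary outcome only: 80% (80% v 20%, 10 per arm), 99% (same rates, 20 per arm) and 85% (65% v 20%, 20 per arm). The pooled-variance formula for two proportions, two-sided 5%, gives 81.7%, 98.9% and 84.9%. These reproduce and do not bear on item 3, for which no power is stated.

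**2. Item 3 beside its neighbours in Section 12.1.2.** Item 2 has a 50% threshold and an interval (baseline to end of PEX). Item 4 requires documentation by imaging. Item 5 uses KDIGO criteria. Item 6 fixes Day 28. Item 3 has no parameter, threshold or day and no rule for discordant or missing tests.

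**3. How much the combining rule matters.** Assume each test shows deterioration with probability p, independently. The documents give no such rate, so p is varied. With k tests, any-test scoring gives 1 − (1 − p)^k and all-test scoring gives p^k.

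| p | one test | any of three | all of three |
|---|---|---|---|
| 10% | 10% | 1 − 0.9³ = 27.1% | 0.1³ = 0.1% |
| 20% | 20% | 1 − 0.8³ = 48.8% | 0.2³ = 0.8% |
| 30% | 30% | 1 − 0.7³ = 65.7% | 0.3³ = 2.7% |

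Real tests would be correlated, which narrows the spread. The direction stays the same: the rate depends on the number of tests done and on an unwritten rule.

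**4. What the analysis choice could cost.** All inputs here are assumptions: log-normal marker, equal log-SD in both arms, correlation ρ between log baseline and log follow-up of 0.5 to 0.7, two-sided 5%. The comparison is a t-test on raw follow-up values against ANCOVA on logs. On the log scale the effect is ln(ratio), for example ln(0.4) = −0.92. The ANCOVA standard error is about SD × √[2(1 − ρ²)/n] per comparison of n against n. Power by simulation, 20,000 runs per setting:

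| Ratio of geometric means | log-SD | n per arm | raw t-test | log ANCOVA (ρ 0.5–0.7) |
|---|---|---|---|---|
| 0.4 | 0.5 | 10 | 95% | 99% or more |
| 0.4 | 1.0 | 10 | 32% | 58–74% |
| 0.4 | 1.0 | 20 | 62% | 90–97% |
| 0.4 | 1.3 | 10 | 16% | 39–52% |
| 0.7 | 1.0 | 10 | 8% | 14–18% |
| 0.7 | 1.0 | 20 | 13% | 24–33% |

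The contrast combines two changes, log scale and baseline adjustment. At ratio 0.4, log-SD 1.0 and 10 per arm, a log-scale t-test without adjustment has 49%, so both contribute. The gain is small when the marker is only mildly skewed. When the effect is modest, both analyses are weak at this sample size.

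**The case against.** The strongest reply is that most of this is already covered. Section 12.4.3 does not prescribe a t-test for item 3. The t-test is an example of what may be done, and the same section says regression will be used for adjusted and repeated-measures analyses. Serial troponin and BNP would fall under that. Worded as prevention of deterioration, the item reads as binary, for which the example is chi-squared. A reader might infer that the plan commits to an inefficient test; it does not.

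A reader might also infer that echo is haphazard throughout, or that the baseline scan in the PEX arm is planned after the first exchange. The documents do not support either. Echo is listed without condition on Days 1 and 7, and the 48-hour scan sits under pre-treatment assessments. What stands is narrower: the plan does not say that the Day 1 scan precedes the exchange.

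A third inference would be that Day 7 markers should replace the whole outcome. That would discard the Day 14 to 28 values and ignore deaths before Day 7, in a setting where Section 12.2.1 cites intensive-care mortality of 48% to 86%. It could also use a sample taken during a second exchange block, which may begin after the Day 5–7 reassessment. A low value then might reflect removal of plasma rather than better function.

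Finally, this is one of six secondary outcomes and carries no power claim. That limits the weight of the point. It does not answer the missing definition.

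**Conclusion.** The point holds as a defect of definition. Item 3 can be scored on different tests in different patients, with no fixed day or combining rule, in an unblinded trial. The size cannot be fixed from the documents. Under the assumed 10–30% per test and independence, the rule alone moves the rate from near zero to between 27% and 66%.

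The analysis half is a recommendation, not an error in the plan. Baseline-adjusted analysis on the log scale is better suited than the one method named for numerical outcomes and is already permitted. Its advantage ranges from a few points to more than 40, depending on a log-SD, correlation and effect that the documents do not give. No particular power loss should be asserted. The primary analysis and sample size are unaffected.

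**What to change.** - **Section 12.1.2, item 3:** remove the and/or. List echo, troponin and BNP as separate components, each reported in all randomised patients with the number observed per arm. Name the echo parameter. If a yes/no deterioration is also wanted, write down its component, cut-off and day before any data are seen.
- **Section 12.4.3:** analyse log troponin and log BNP by regression adjusting for the marker's own pre-exchange Day 1 value, using either ANCOVA at Day 7 or a repeated-measures model over the scheduled days. State which. Report the ratio of geometric means with a 95% confidence interval.
- **Sampling:** state that these samples are taken before any exchange given that day, and settle whether Day 5 is a sampling day (Section 9.4.1 and Appendix 3 differ).
- **Deaths and missing values:** state how deaths before the time point are handled, and what is done when echo is missing.
- **Echo:** report the paired change from the Day 1 pre-exchange scan to Day 7, with numbers scanned per arm. Align the Day 28 entry in Section 9.4.1 with Appendix 3.

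The cost is wording and slightly more analysis work, since the samples and the Day 1 and Day 7 scans are already scheduled. Separate components mean more comparisons, so the optional multiplicity adjustment in Section 12.4.3 should be settled at the same time.

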12.2 Sample size and recruitment

12.2.1 Sample size calculation

Mortality of patients on intensive care with COVID-19 has been reported to range from 48% of patients no longer on ITU (ICNARC report on COVID-19 in critical care, 27 Mar 2020) to 86% of patients who required invasive mechanical ventilation (Yang, Lancet Respiratory Medicine, Feb 2020).

We aim to recruit up to 40 patients in total (20 per arm). We will have 80% power to detect a statistically significant difference between the treatment groups at the 5% level assuming that PEX+SOC will reduce inflammation markers in 80% of patients compared to just 20% for SOC if we recruit 20 patients. The power is increased to 99% if 40 patients are recruited. Alternatively, if the effect is lower, e.g. PEX+SOC reduces markers in 65% of patients, then the power will be 85% based on 40 patients.

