To compare the stability of cardiac function based on echocardiogram/troponin/BNP measurements cardiac function between Plasma Exchange (PEX) and control groups in patients with severe COVID

To compare incidence of acute kidney injury as defined by KDIGO criteria between Plasma Exchange (PEX) and control groups in patients with severe COVID

To compare mortality at day 28 between the PEX and control groups

Type of trial: A Phase II, Parallel-group, unblinded, randomised controlled trial in COVID 19

Trial design and methods: Patients will receive standard of care (SOC), or SOC and PEX. Single volume PEX capped at 3 litres if <100Kg and 4 litres if >100Kg. PEX will be given once a day for a minimum of 5 days. The course can be repeated at the discretion of the treating clinician, depending on patient's response based on a reassessment on D5-7, where there is clinical and biochemical improvement following initial 5-day block but persistent pro-thrombotic phenotype ie 5 days initial block plus reassess.

Data collection includes routine laboratory parameters, FBC, renal function and liver function; inflammatory markers (D Dimers, LDH, CRP) and pre and post PEX samples to measure von Willebrand factor (VWF) and ADAMTS13 activity levels. The latter samples will be stored for further investigation related to COVID, for example, COVID19 viral analysis, cytokines.

The control patients will have citrate and serum samples taken daily. Following the initial 5 day period. If patients have more than one 5 block of PEX, comparable daily samples will be taken. Thereafter, weekly to day 28.

Trial duration per participant:	From consent to 28 days
Estimated total trial duration:	From when first participant enrolled to last participant follow-up.
Planned trial sites:	Single-site
Total number of participants planned:	Minimum 20, maximum 40

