9.9 Stopping rules

The trial may be stopped before completion for the following reasons:

Anaphylaxis to plasma during PEX

On the recommendation of the TMG

On the recommendation of the sponsor and CI

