9.10 Definition of End of Trial

The end of trial is day 28 of the last participant.

10 Recording and reporting of adverse events and reactions

Collection, recording and reporting of adverse events (including serious and non-serious events and reactions) to the sponsor will be completed according to the sponsor's SOP (INV/S05).

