14.1 Trial Management Group (TMG)

The TMG will include the Chief Investigator and trial staff. The TMG will be responsible for overseeing the trial. The group will meet regularly monthly and will send updates to PIs.

The TMG will review recruitment figures, SAEs and substantial amendments to the protocol prior to submission to the REC and/or MHRA. All PIs will be kept informed of substantial amendments through their nominated responsible individuals.

15 Direct Access to Source Data/Documents

The investigator(s)/ institution(s) will permit trial-related monitoring, audits, REC review, and regulatory inspection(s), providing direct access to source data/documents. Trial participants are informed of this during the informed consent discussion. Participants will consent to provide access to their medical notes.

16 Ethics and regulatory requirements

The sponsor will ensure that the trial protocol, participant information sheet, consent form, submitted supporting documents have been approved by the appropriate regulatory body (MHRA in UK) and an appropriate research ethics committee, prior to any participant recruitment. The protocol, all other supporting documents including and agreed amendments, will be documented and submitted for ethical and regulatory approval as required. Amendments will not be implemented prior to receipt of the required approval(s).

An annual progress report (APR) will be submitted to the REC within 30 days of the anniversary date on which the favourable opinion was given, and annually until the trial is declared ended. The chief investigator will prepare the APR.

Within 90 days after the end of the trial, the CI/Sponsor will ensure that the main REC and the MHRA are notified that the trial has finished. If the trial is terminated prematurely, those reports will be made within 15 days after the end of the trial.

The CI will supply the Sponsor with a report of the clinical trial which complies with the format as defined by the EMA. This will then be uploaded to EudraCT for availability to the MHRA and a copy of the report will be submitted to the main REC, within 1 year after the end of the trial.

The study will be reviewed and authorised to proceed through urgent regulatory review by UCLH COVID19 Clinical trial group

17 Monitoring requirement for the trial

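### Does the 20-to-40 recruitment range, with no definition of completion, leave the primary test open to results-driven closing?

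*Combined protocol and SAP*

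**What the plan says.** The synopsis plans a total of "Minimum 20, maximum 40". Section 12.2.1 says "We aim to recruit up to 40 patients in total (20 per arm" and gives power at two totals only: 80% at 20 patients and 99% at 40 for response rates of 80% against 20%, and 85% at 40 for 65% against 20%. Section 12.2.2 has recruitment run for as long as the pandemic does. Section 12.5 plans no interim analysis, and 12.4.2 describes one chi-squared comparison.

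Section 9.9 opens "The trial may be stopped before completion for the following reasons" and lists anaphylaxis, a recommendation of the Trial Management Group (TMG), and "On the recommendation of the sponsor and CI". No ground is attached to the last two. Section 9.10 states only that "The end of trial is day 28 of the last participant". Section 16 allows 90 days to notify the end of the trial, but adds: "If the trial is terminated prematurely, those reports will be made within 15 days after the end of the trial".

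On who sees what: the trial is unblinded (6.1); "The TMG will include the Chief Investigator and trial staff" (14.1); section 11.4 has reviewed data presented to the TMG; and the Day 5-7 reassessment in 9.4.1 is a "Review of clinical and laboratory parameters by trial team".

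**The concern.** A planned range instead of a fixed number leaves the final total to be settled during the trial. Here the people who could settle it are unblinded investigators. They see CRP, LDH and D dimer patient by patient, and they receive trial data without any statement that these are pooled over arms. If they closed recruitment when the difference looked favourable, the single 5% test at the end would in effect be one of several looks, and its true error rate would exceed 5%. No sentence rules this out.

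The second worry concerns wording. Section 9.9 speaks of stopping before completion and section 16 of premature termination, yet neither term is tied to a number. A trial that closes at 26 has passed the minimum but not the figure aimed for. A reader could call it complete or stopped early, and the notice period would differ accordingly.

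**Working it through.** **1. The plan's own figures.** Inputs from 12.2.1: two-group comparison at the 5% level (two-sided assumed, since sidedness is not stated), 1:1 allocation, n = 10 or 20 per arm. With pbar = (p1 + p2)/2,

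power = Phi{ [ |p1 - p2| - 1.96 x sqrt(2 pbar(1 - pbar)/n) ] / sqrt( p1(1 - p1)/n + p2(1 - p2)/n ) }.

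- 80% v 20%, n = 10: (0.600 - 1.96 x 0.2236)/0.1789 = 0.904, power 81.7% (stated 80%).
- 80% v 20%, n = 20: (0.600 - 1.96 x 0.1581)/0.1265 = 2.29, power 98.9% (stated 99%).
- 65% v 20%, n = 20: (0.450 - 1.96 x 0.1563)/0.1392 = 1.03, power 84.9% (stated 85%).

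Exact power of the uncorrected chi-squared test is 80.5%, 98.2% and 84.1%. All stated figures hold within 2 points.

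**2. Type I error when the total does not depend on results.** For n per arm and a common response rate p, sum the binomial probabilities of all pairs (a, b) for which (a - b)²/n² divided by 2 pbar(1 - pbar)/n is at least 3.84, where pbar is now the observed pooled proportion (a + b)/(2n). For p from 20% to 50%:

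| Total | Type I error |
|---|---|
| 20 | 2.99-4.22% |
| 26 | 4.29-7.56% |
| 40 | 4.25-5.34% |
| any single even total from 20 to 40 | 2.99-7.56% |

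If the closing total N is independent of the outcomes, the overall error is the sum over n of P(N = n) x error(n). It is an average of single-total values and cannot exceed the largest of them. The 7.56% (total 26, rate 50%) comes from the discreteness of the uncorrected test in small samples. It is not caused by an open total, and a sentence about closing rules would not alter it.

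**3. What results-driven closing would cost.** This assumes looks that no section plans. Unadjusted 5% tests at 20 and again at 40 give 6.89-7.71% for rates of 20-50%, 6.14% at 15%, 4.34% at 10% and 1.21% at 5%. With a continuity correction the figure stays below 3%. Testing after every pair of patients from 20 to 40 gives about 10.8-13.8% (simulated at rates of 20%, 30% and 50%). The hypothetical damage is therefore real but needs repeated between-arm testing.

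**4. Does any section provide for such looks?** Section 12.5 excludes a planned one. Section 12.2.2 points to an external reason for closing. The TMG's listed business in 14.1 is recruitment figures, SAEs and substantial amendments; efficacy is not on it. The Day 5-7 review in 9.4.1 considers whether an individual patient has a further block of plasma exchange; it is not a comparison of arms. Section 11.4 sends reviewed data to the TMG without saying they are masked by arm, but it describes no test.

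**5. Completion and notice.** Neither 9.9 nor section 16 mentions a patient number. Read with the synopsis and 12.2.2, a total inside 20 to 40 reached because the pandemic waned lies within the plan, and a stop recommended under 9.9 does not. If the sponsor is unsure, a notice within 15 days meets both limits, since 15 is less than 90. Under either label the end of trial is dated the same way (9.10) and the intention-to-treat analysis is the same (12.4.2).

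**The case for a change.** The best case for acting is that silence in an open-label trial with a flexible total invites doubt. Section 12.5 rules out a planned look, but it does not say on what basis recruitment may close short of 40. The TMG consists of trial staff, it receives data not described as masked, and its recommendation to stop needs no stated ground. A few sentences would let a reader of a trial that closed at 26 see that the number was not chosen on the results, and would settle the notice period at no cost in patients or analyses.

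It is true that neither completion nor independence from results is written down, and section 11.4 does widen what the TMG may see. But the extra sentences would only promise not to do something the protocol nowhere plans. They would not stop unblinded staff noticing marker trends informally. Nor is the wording free of risk. Naming 40 as the target in 12.2.1 alone would contradict the range in the synopsis. A blanket bar on closing because of between-arm marker results would also bind the TMG, the only oversight committee described, unless safety were exempted.

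**Conclusion.** The concern identifies missing detail, not an error. Followed as written, the plan yields one primary test on a total set by recruitment. At 40 patients its type I error is 4.3-5.3% for common response rates of 20-50%, and the stated powers are right. The 6.9-7.7% for looks at 20 and 40 belongs to a conduct the protocol does not describe and is no evidence against the planned test. The remaining ambiguity is a 15-day against a 90-day notice, with no effect on the estimate, its interval or the p-value. Whoever reports the trial can fill the gap by giving the date, the total and the reason recruitment closed.

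This rests on three assumptions: equal arms, a two-sided uncorrected chi-squared test, and closing that follows 12.2.2 and 12.5. If the trial's records showed that arms had been compared on the markers before recruitment closed, the figures in step 3 would become relevant and the conclusion would need to be revisited. A total near 20 would also carry low power for the smaller effect (65% against 20%): 53.4% by the formula in step 1, or 52.2% exactly. That is a consequence of the range the sponsor chose and does not bear on the validity of the test.
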